### *Secondary Outcome Measures*

2. Fever changes over time (body temperature change on days 2-7 compared to baseline).
3. Average duration of fever.
4. Proportion of subjects with normal body temperature (below 37,0^0C) on days 2-7.
5. Severity of clinical manifestations of influenza (fever, general symptoms and nasal/throat/chest symptoms) in scores on day 1-7 – according to the patient's diary; on days 1, 3 and 7 – according to objective examination by the investigator.

---

 **Recovery criteria:** body temperature <37.0^0C + no symptoms.

**Improvement criteria:** body temperature ≤37.2C + total symptom score (except for fever index) ≤2 scores.

 Criteria of no fever - body temperature lower than 37.0° C for 24 hours.

6. Duration of the major clinical symptoms of influenza (fever, general symptoms and (nasal/throat/chest symptoms) in days (according to the patient diary).
7. Severity of influenza course (based on area under curve for total influenza severity score on days 1-7 – according to the patient diary; on days 1, 3 and 7 – according to objective examination by the physician).
8. Proportion of patients, who used antipyretics on days 1, 2, 3, 4 and 5 of the treatment.
9. Proportion of patients with complications requiring antibiotics, aggravation of the disease (severe influenza).
10. Proportion of patients with negative results of virology assay on days 3, 5 and 7 (based on PCR of nasopharyngeal swabs).
11. Dynamics of Parameters of Immune Status (T-cell and B-cell Immune Response) on days 1, 3 and 7 of the observation:
  - Concentration of regulators of the T-cell immune response (IL2, IFN  $\gamma$ , IL-18), and regulators of B-cell immune response (IL-4, IL-16).
12. Dynamics of Parameters of Immune Status ( IFN- $\alpha$  and IFN- $\gamma$  Production) on days 1, 3 and 7 of the observation:
  - Level of spontaneous and induced production of IFN- $\alpha$  and IFN- $\gamma$  by leukocytes (in vitro).
13. Dynamics of Parameters of Immune Status (Absolute Number of Each Type of White Blood Cells and Different Lymphocyte Phenotypes) on days 1, 3 and 7 of the observation:
  - The absolute number of each type of white blood cells (WBC): Absolut Count (AC) of leukocytes, neutrophils, lymphocytes, monocytes, eosinophils, basophils, and CD3, CD4, CD8, CD4/CD8, CD16, CD119 leukocytes.

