14. Dynamics of Parameters of Immune Status (relative percentage of each type of white blood cells and different lymphocyte phenotypes) on days 1, 3 and 7 of the observation:
  - The relative percentage of each type of white blood cells (WBC): Relative Count (AC) of leukocytes, neutrophils, lymphocytes, monocytes, eosinophils, basophils, and CD3, CD4, CD8, CD4/CD8, CD16, CD119 leukocytes.

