## **Study design**

Study design: an open-label, comparative, randomized, parallel group clinical study to evaluate efficacy of the study treatment.

The study will enroll outpatient subjects of either gender aged 18-70 years old inclusively with clinical manifestations of influenza during seasonal morbidity seeking medical advice within the first two days of the disease.

After signing informed consent to participate in the clinical study baseline examination will be initiated including nasal swab for rapid diagnosis and verification of influenza as the cause of the disease. In case of positive result of immunochromatographic test the patient will be enrolled. In case of negative result of rapid test the patient will be enrolled provided that (1) he/she has clinical manifestations of typical influenza; (2) the history evidences contact with a patient with influenza; (3) the region has influenza epidemics. Additionally, at the screening (Day 1) all patients regardless of the results of rapid test will provide nasopharyngeal swabs for further PCR diagnosis and identification of RNA of influenza A and B virus, thermometry, history collection, evaluation of vital signs, physical examination will be performed and concomitant therapy will be recorded. Females of childbearing potential will undergo pregnancy test. If inclusion criteria are met and non-inclusion criteria are absent (Day 1) the patient will be enrolled in the trial and randomized into one of the two groups: group 1 will receive Ergoferon as per the selected dosing regimen for 5 days; group 2 will be treated with Oseltamivir at 75 mg twice a day for 5 days.

At Day 1 visit the patient will receive the study product and an antipyretic product approved by the study protocol.

The patient will receive the diary in which he/she will have to record axillary body temperature (measured by non-mercuric Geratherm Classic thermometer ) in the morning and evening as well as intensity of the disease symptoms and number of doses of the antipyretic product. The investigator will train the patient concerning the diary filling.

In total 3 visits (Days 1, 3 and 7) will be made by the patient/investigator during the treatment and follow-up period, on day 5 an additional visit will be made for nasopharyngeal swabs.

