At Day 1, Day 3 and Day 7 visits blood sampling will be made for immunological tests at the investigator's discretion. At Day 3 and Day 7 visits the investigator will collect complaints, document examination findings, intensity of influenza symptoms in scores, control the prescribed and concomitant medications, assess safety of the study therapy and check the patient's diary. Furthermore, nasopharyngeal swabs (Days 1, 3, 5, 7) and blood samples (Days 1, 3, 7) will be made for lab tests. The total observation period will be 7 weeks (screening, randomization – 1 day, treatment – 5 days, follow-up – 2 days). The patient will keep diary throughout the whole 7-day observation period.

Symptomatic therapy of influenza and co-morbidities will be allowed except for the products specified in “Forbidden concomitant therapy” section.

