### Study design scheme

### Schedule of study procedures

Procedure/visit	Day 1	Day 3	Day 5	Day 7
Obtaining informed consent (signing informed consent by the patient)	+			
Collection of complaints	+	+		+
Collection of medical history data	+			
Objective examination	+	+		+
Recording influenza symptoms in scores	+	+		+
Collection of nasal swabs and isolation of influenza agent antigens	+			
Collection of nasopharyngeal swab for PCR diagnosis	+	+	+	+
Pregnancy test	+			
Information on concomitant medicines	+	+		+

Inclusion/exclusion criteria	+			
Randomization and prescription of study therapy	+			
Antipyretic drug dispensing	+			
Blood sampling for immunological tests	+	+		+
Dispensing of the study drug	+			
Drug accountability and return, assessment of compliance				+
Distribution of diaries	+			
Evaluation of correct diary filling		+		+
Diary return				+
Evaluation of therapeutic safety		+		+

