## Statistical Analyses

### *Samples*

Total set comprised all enrolled patients whose parents/adopters had signed the informed consent form for participation of a patient in the trial. This sample will consider all adverse events throughout the study, including those occurred prior to the study therapy. Any medically unfavourable events (conditions) recorded in patients from Total set after signing informed consent but before administration of the study product will be considered as concomitant conditions.

Sample of the patients receiving at least one dose of the study product will be used for the study drug safety assessment (Safety population), as any adverse events emerging after administration of the product will be recorded.

Full Analysis Set This sample will consist of all enrolled patients, except for those who met at least one of the following criteria:

- 1) failure to meet inclusion/non-inclusion criteria;
- 2) patient failing to take any dose of the study drug;
- 3) absence of any data on the patient after randomization.

This was the best set for the Intention-to-treat method, so it will be used in the Intention-to-treat efficacy analysis of the test therapy.

Unavailable/missing data (parameters/variants) will be completed by the Last Observation Carried Forward method (LOCF).

Per Protocol set. This sample includes all patients who completed the therapy as per the study protocol, without any missing visits or major protocol deviations. This set will be used in the Per Protocol efficacy analysis of the test therapy.

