### *Evaluation of sample size*

The sample size was assessed in accordance with the following rules and assumptions:

1. Statistical assumptions:

- 1.1 Lack of clinically relevant superiority of reference product (oseltamivir) over test product (Ergoferon) is assumed, thus statistically meeting Non-Inferiority design:

$$\mathbf{H_0: Ef_{control} - Ef_{test} \geq \delta}$$

$$\mathbf{H_A: Ef_{control} - Ef_{test} < \delta,}$$

where  $\mathbf{Ef_{control}}$  – effect of reference product (oseltamivir),  $\mathbf{Ef_{test}}$  – effect of test product (Ergoferon),  $\delta$  – clinically relevant difference;

- 1.2 Clinically relevant difference value “ $\delta$ ” is considered to be equal to 20% (i.e. Ergoferon effect is supposed to be comparable to the one of oseltamivir if the effect of test product is superior to or inferior to the effect of reference product by no more than 20%);
- 1.3 The power of statistical tests ' $P = (1 - \beta)$ ' is 80% (the probability of correct rejection of the null hypothesis is 0.8);
- 1.4 The probability of type 1 error ' $\alpha$ ' is less than 5% (the probability of false acceptance of the alternative hypothesis is less than 0.05);
- 1.5 Therefore, sample size will be calculated taking into account:
- a. assumption on expected effects declared in the main efficacy criterion of the protocol;
- 1.6 calculation of sample size of groups 1 and 2 for two-sided test for final analysis will be made using the formula:

$$\mathbf{N_1=N_2=(p_a(1 - p_a) + p_b(1 - p_b)) I,}$$

where  $\mathbf{N_1}$  and  $\mathbf{N_2}$  – samples sizes in Ergoferon and Oseltamivir groups

$\mathbf{p_a}$  and  $\mathbf{p_b}$  – expected proportions of the patients with recovery/improvement in these groups

$\mathbf{I}$  – Fisher's information detected using the formula:

$$\mathbf{I=(z_\alpha + z_\beta)^2/(\theta - \delta)^2,}$$

where  $\mathbf{z_\alpha}$  and  $\mathbf{z_\beta}$  – tabular values of z-test for  $\alpha$  and  $\beta$ ,  $\theta$  – difference between proportions ( $\mathbf{p_a - p_b}$ ),  $\delta$  – clinically relevant difference;

- 1.7 final sample size will be determined using the formula:

$$\mathbf{N_F = N / (1 - K_B),}$$

---

 SAS/STAT(R) 9.2 User's Guide, Second Edition.

[http://support.sas.com/documentation/cdl/en/statug/63033/HTML/default/viewer.htm#statug\\_seqdesign sect027.htm](http://support.sas.com/documentation/cdl/en/statug/63033/HTML/default/viewer.htm#statug_seqdesign sect027.htm)

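### Discretionary immunology blood sampling conflicts with the schedule and leaves the comparison of immune outcomes 11–14 unprotected against arm-dependent selection

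*Combined protocol and SAP*

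**What the plan says.** The narrative in Study design states that on Days 1, 3 and 7 "blood sampling will be made for immunological tests at the investigator's discretion". Shortly afterwards the same section says, with no condition, that "nasopharyngeal swabs (Days 1, 3, 5, 7) and blood samples (Days 1, 3, 7) will be made for lab tests".

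In the Schedule of study procedures, the row "Blood sampling for immunological tests" carries a plus sign at Days 1, 3 and 7, with no footnote and no subset.

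Secondary outcomes 11 to 14 depend on this blood. Outcome 11, for example, is "Dynamics of Parameters of Immune Status (T-cell and B-cell Immune Response) on days 1, 3 and 7 of the observation". Outcomes 12 to 14 (interferon production, absolute cell counts, relative cell counts) use the same days. None is restricted to a subset. They are four of the thirteen secondary outcomes, which are numbered 2 to 14.

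The trial is described as "an open-label, comparative, randomized, parallel group clinical study". The Samples section defines the Total, Safety, Full Analysis and Per Protocol sets and no immunology set. Its only rule for missing values is last observation carried forward. The plan gives no criterion for choosing patients for sampling and no target number.

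**The concern.** Randomisation makes the arms comparable for all patients randomised. It makes a sampled subset comparable only if being sampled does not depend on arm and prognosis together. Here the person who may decide on the draw knows the treatment. At Days 3 and 7 that person has also collected complaints, scored symptoms and checked the diary at the same visit. If investigators tended to sample the sicker patients in one arm and not in the other, a difference in immune parameters could appear without any treatment effect, in a direction that cannot be predicted.

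Carrying values forward does not solve this. A patient never sampled has nothing to carry forward, and one sampled only on Day 1 would be credited with zero change in an outcome that is about change.

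There is also a loss of precision. Fewer samples make the immune comparison weaker even when selection is harmless.

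**Working it through.** **The plan's own figures.** The recruitment target reproduces: 158 / (1 − 0.20) = 197.5, rounded up to 198; 79 / (1 − 0.20) = 98.75, rounded up to 99 per group. These figures serve the primary outcome. No number is planned for immunology, so the check below takes 79 completers per arm as the ceiling.

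**Inputs from the plan.** 79 completers per arm (Number of patients); a two-sided test, 80% power and alpha 0.05, described as "the probability of false acceptance of the alternative hypothesis is less than 0.05" (Evaluation of sample size). Using the same alpha and power for the immune outcomes is an assumption, because the plan sets none for them.

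**Assumptions not in the plan.** A fraction f of each arm is sampled. One arm is sampled at random. In the other, selection has correlation r with the immune response. There is no treatment effect, and the response has SD 1.

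**Formulas.** With z the normal quantile of f and φ the normal density:
- bias in SD = r × φ(z) / f
- non-centrality nc = bias × √(79f / 2)
- false-positive rate = P(|Z + nc| > 1.96)

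For f = 0.5 and r = 0.2: φ(0) / 0.5 = 0.399 / 0.5 = 0.798; bias = 0.2 × 0.798 = 0.16 SD; √(39.5 / 2) = 4.44; nc = 0.71; rate = 11%.

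| Fraction sampled | r = 0.1 | r = 0.2 | r = 0.3 |
|---|---|---|---|
| 30% | 7% | 13% | 22% |
| 50% | 6% | 11% | 19% |
| 75% | 6% | 7.5% | 11% |
| 90% | 5% | 6% | 6% |

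**Other patterns, half sampled in each arm.**
- Same rule and same strength in both arms: the biases cancel, and the rate stays at 5%.
- Same direction, r = 0.3 against 0.2: bias = 0.1 × 0.798 = 0.08 SD, nc = 0.35, rate about 6.5%.
- Opposite directions, r = 0.2 in each: bias = 2 × 0.16 = 0.32 SD, nc = 1.42, rate about 29%.

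**Precision without any bias.** Detectable difference = (1.96 + 0.84) × √(2 / n), with n sampled per arm:
- all sampled, n = 79: 0.45 SD
- 75% sampled, n = 59.25: 0.51 SD
- 50% sampled, n = 39.5: 0.63 SD
- 25% sampled, n = 19.75: 0.89 SD

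Power for a true difference of 0.45 SD falls from 81% with everyone sampled to 69%, 52% and 29% at these three reduced fractions.

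**The case against.** The best defence is that the discretion phrase stands alone. The later sentence in Study design, the schedule and outcomes 11–14 all point to sampling everyone. Discontinuation criterion 2 treats departures from the laboratory sampling schedule as serious, and the Per Protocol set excludes missed visits and major deviations. The phrase may be a drafting slip, or it may mean discretion over which immunological tests are run and not over which patients are bled. This makes a freely chosen subset less likely. It does not remove the phrase, and the plan does not say whether a sample omitted by discretion counts as a deviation. Sites may follow the narrative.

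Timing also matters. These outcomes are changes from Day 1, when early response is unknown, and the plan does not say whether the Day 1 draw comes before or after randomisation. If it comes before, only the decisions at Days 3 and 7 could depend on arm. That point stands and narrows the exposure without closing it.

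A reader might infer that the randomised comparison is lost for these outcomes and that no analysis could repair it. The documents do not support that. Bias needs selection that differs between arms, and nothing shows that investigators would select in that way. Comparing sampled with unsampled patients at baseline, weighting and sensitivity bounds could address part of any problem, although not selection for unrecorded reasons.

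**Conclusion.** The conflict in the text is certain; the bias is only possible. As written, the plan permits sampling that depends on arm and early response in an open-label trial, and it contains nothing that would prevent this. The comparison of outcomes 11–14 is therefore unprotected, which is a narrower conclusion than saying it is invalid.

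The size depends wholly on how the discretion is used. With one-arm selection at r = 0.2 to 0.3, the false-positive rate per parameter is about 11–19% with half sampled, about 7.5–11% with three quarters sampled, and close to nominal with 90% sampled. The fractions and correlations are assumptions, since the plan supplies neither. The precision loss at half-sampling, 0.45 to 0.63 SD, needs no assumption about selection.

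The primary outcome, the sample size and the clinical, virological and safety outcomes are not touched. The point should be corrected before enrolment, because samples not drawn cannot be recovered.

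**What to change.** Reconcile the Study design narrative with the Schedule of study procedures in one of two ways.

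1. Delete the discretion phrase, so that every randomised patient has blood drawn for immunology on Days 1, 3 and 7 as the schedule already shows.
2. If laboratory capacity is limited, define a subset before allocation is known, such as named sites or the first consecutive patients at each site. State its size, draw all three samples in it, and define a matching immunology analysis set.

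In either case, report the numbers sampled by arm and visit, and say whether a sample omitted by discretion is a protocol deviation.

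The first option is a wording change and adds nothing to the published schedule. If the sponsor had meant to sample only some patients, it means more laboratory work: 158 × 3 = 474 draws among completers, including the in vitro interferon tests. The second option needs no extra samples but keeps the lower precision of a subset. Both leave sites less freedom.

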## **Inclusion and exclusion criteria**

### ***Inclusion criteria***

1. Patients aged from 18 to 70 years.
2. Patients who were admitted to hospital within 48 hours from the onset of influenza signs.
3. Patients with body temperature  $\geq 37.8^{\circ}\text{C}$  when visiting a doctor + severity of influenza symptoms  $\geq 4$  scores (presence of at least one general symptom  $\geq 2$  scores and 1 nasal/throat/chest symptom  $\geq 2$  scores or greater number of symptoms with the severity  $\geq 1$  point).
4. Diagnosed influenza confirmed by rapid diagnostic test (OSOM Influenza A&B Test).
5. The possibility to start therapy after the onset of the first symptoms of influenza.
6. Usage of contraceptive methods by both gender patients of reproductive age during the trial and within 30 days after ending the participation in the trial.
7. Availability of signed patient information sheet (Informed Consent form) for participation in the clinical trial.

### ***Exclusion criteria***

1. Suspected pneumonia, bacterial infection or the presence of a severe disease requiring usage of antibacterial drugs (including sulphanilamides) starting from Day 1 of the disease.
2. Severe influenza with indications for hospitalization.
3. Suspected early manifestations of diseases that have symptoms similar to influenza symptoms (other acute respiratory and infectious diseases, influenza-like syndrome at the onset of systemic connective tissue disorders, hematologic neoplasms and other pathology).
4. Patients requiring concurrent antiviral products forbidden by the study.
5. Medical history of primary and secondary immunodeficiencies. a) lymphoid immunodeficiencies (T-cell and/or B-cell, immunodeficiencies with predominant antibody deficit); b) phagocytic deficits; c) complement factor deficit; d) combined immunodeficiencies including AIDS secondary to HIV infection; toxic, autoimmune,

---

 Severe influenza criteria (RF MoH, 2009; WHO 2014; CDC 2009-2014): Extreme degree of general intoxication syndrome (toxic shock III, vomiting, dehydration symptoms, reduced diuresis/anuria, restlessness or abrupt weakness up to complete adynamia, tachypnea, tachycardia inconsistent with temperature, convulsions, meningism symptoms), cognitive disorders, hemorrhagic syndrome (epistaxis, dermal and mucosa petechiae), hemodynamic instability, expressed obstructive disorders (stenosing laryngotracheitis, bronchial obstruction syndrome), acute respiratory failure, primary and secondary pneumonia. Risk factors for severe influenza and complications: chronic cardiovascular, respiratory diseases, diabetes mellitus, immunodeficiencies, oncology.

infectious, radiation panleukopenic syndrome; total lymphocytopenic syndrome; polyclonal lymphocyte activation syndrome; postsplenectomic syndrome; congenital asplenia; abnormal immune complex syndrome associated with infectious, autoimmune and allergic diseases.

6. Medical history of sarcoidosis
7. An oncological disease/suspected oncological disease.
8. Exacerbated or decompensated chronic diseases affecting a patient's ability to participate in the clinical trial.
9. Medical history of polyvalent allergy.
10. Allergy/intolerance to any of the components of the product used for influenza therapy.
11. Impaired glucose tolerance, type 1 and type 2 diabetes mellitus.
12. Malabsorption syndrome, including congenital or acquired lactose deficiency or another disaccharide deficiency.
13. Pregnancy, breast-feeding.
14. Consumption of narcotics, alcohol > 2 alcohol units per day, mental diseases.
15. Use of any medicine listed in the section "Prohibited concomitant treatment" within 30 days preceding the inclusion in this study.
16. Patients who, from the investigator's point of view, will fail to comply with the observation requirements of the trial or with the regimen of the study drugs.
17. Participation in other clinical studies within 1 month prior to enrollment in the current trial.
18. Patients related to the research staff of the clinical trial site who are directly involved in the trial or are the immediate family member of the researcher. The immediate family members include husband/wife, parents, children or brothers (or sisters), regardless of whether they are natural or adopted.
19. Patients employed with OOO "NPF "MATERIA MEDICA HOLDING" (i.e., the company's employee, part-time employee under contract, or appointed official in charge of the trial, or their immediate family).

### **Discontinuation criteria**

1. Participant's failure or decline to comply with the protocol requirements.
2. Deviation from the schedule of examinations and sampling for lab tests by  $\geq 1$  day.
3. The necessity to use medications not permitted in the study.
4. An adverse event requiring discontinuation of the study drug.
5. Patients who decide to withdraw early from the study due to lack of treatment efficacy or for any other reason.

6. Cases not stipulated in the protocol where the investigator decides that further participation may harm the patient.
7. Eligibility error.

